#### Sampling technique:

In this study we will use a multi-stage stratified random sampling technique.

-At the educational offices level: All three educational offices will be included.

-At kindergarten level: Cluster sampling using stratified proportional sampling technique. This study will include ten kindergartens. The number of kindergartens was determined based on a comprehensive assessment, taking into consideration each educational office's weight and the extent of its children enrollment. This method will ensure that the sample size from each office is distributed proportionally by accounting for the public and private strata.

To select kindergartens from each education office, we will use the Simple Random Sampling (SRS) technique. The names of kindergartens will be listed, assigning a number to each KG. A computer random numbers generator will be used to randomly select KGs to be invited to take part in the study.

#### **1-Al-Hofuf Education office:**

#### **Public kindergartens:**

A list of all 46 public kindergartens in Al-Hofuf was obtained. A computer random number generator will be used to randomly select five kindergartens in the following manner: 1- The number of children in each kindergarten varies from 10 to 212; thus, Al-Hofuf kindergartens will be divided into three groups based on the number of children enrolled. 2-Each group will consist of approximately 15-16 kindergartens.

3-One kindergarten will be randomly selected from each group using a computer random number generator.

#### **Private kindergartens:**

A list of all 24 private kindergartens in Al-Hofuf was obtained. A computer random number generator will be used to randomly select two kindergartens in the following manner: 1- The number of children in each kindergarten varies from 5 to 128; thus, Al-Hofuf kindergartens will be divided into two groups based on the number of children enrolled. 2-Each group will consist of 12 kindergartens.

3-One kindergarten will be randomly selected from each group using a computer random number generator.

This procedure for KGs selection will be applied in all educational offices.

Sampling fraction= 14/149 = 0.09. The probability of each KG to be selected is 9%. Study weight= 149/14 = 11. Each KG will represent 11 KGs.

#### -Classroom and children level:

The selection of classes from each KG will be conducted in the following manner:

-The total number of classes in each KG will be determined.

-The number of children enrolled in each class will be determined.

\*If the number of classes and/or children fulfills the sample size, all of them will be included.

\*If the number of classes and/or students exceeds the required sample size, simple random sampling techniques will be used.

#### -At the classroom level:

Using a lottery.

#### -At the children level:

Using a computerized random number generator.

Classes will be randomly allocated into the two study groups (conventional and nonconventional) using a a coin toss.

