#### **Inclusion criteria:**

-Children aged 5-6 years who are registered in the respective academic year at kindergarten

schools in Al-Ahsa.

-Mothers of preschool children who agree to participate and provide consent.

-Children and mothers who can attend all educational sessions.

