#### **Measurements:**

**1- Children's plaque index** will be measured using simplified oral hygiene index (S-OHI). The plaque scores will be recorded according to the (S-OHI) to assess oral hygiene status for children. The oral examination will be performed using a sterilized disposable examination kit, including a mouth mirror and explorer, in a separate classroom with each student seated on a chair under optimum artificial light.

The examiners will perform an oral examination for children in both groups and record their plaque score before the intervention and after 3 months of intervention. Oral examination will be conducted in the morning hours before the school meal. Children will not be informed about the day of examination to prevent **Hawthorne effect**. **Hawthorne Effect:** It is a psychological phenomenon that occurs when individuals modify their behavior or performance in response to the awareness of being observed.

**2-Mothers' oral hygiene knowledge, attitudes, and practices towards their children**, using a questionnaire. Paper questionnaire will be submitted before the intervention and after 3 months of intervention.

3-Demographic information, parents' socioeconomic condition, dietary habits and oral hygiene performance to reduce confounding factors, using a self-administered questionnaire to complete at home and return to the researchers before conducting the study.

(Accounting for the cultural sensitivity self-administered parental questionnaire will be used. Before conducting the study, the validity and practicality of the questionnaire will be tested.) Evaluations of children's oral hygiene status and mothers' knowledge, attitude and practices toward their children will be recorded before the intervention and after 3 months of intervention for the two groups.

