### **Ethical considerations**

This study will obtain approvals from:

-Internal Research Board (IRB) Approval from internal department of college of dentistry.

-Deanship of Scientific Research Approval from King Faisal University (KFU).

-Formal Approval from Ministry of Education (MOE).

-Formal Approval from each kindergarten (KG) administration.

-Informed consent from each child's guardian.

Participant's confidentiality will be protected. Research data will be preserved by using participant codes in all data and will be stored securely.

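### Consent, eligibility and baseline are not placed before the class coin toss, so pairs can be enrolled and mothers can report baseline with the arm already known

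*Protocol*

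**What the plan says.** Allocation is described in the Protocol's sampling procedure, under the heading on the children level: "Classes will be randomly allocated into the two study groups (conventional and nonconventional) using a a coin toss". One toss fixes the arm of every mother-child pair in a class.

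Baseline is anchored to the intervention. In Measurements, examiners will "record their plaque score before the intervention and after 3 months of intervention", and for mothers, "Paper questionnaire will be submitted before the intervention and after 3 months of intervention". The same section sums up: "Evaluations of children's oral hygiene status and mothers' knowledge, attitude and practices toward their children will be recorded before the intervention". The background questionnaire (demographics, socioeconomic condition, diet, oral hygiene performance) has a different anchor; it is collected "using a self-administered questionnaire to complete at home and return to the researchers before conducting the study".

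Consent appears twice, without a time. Inclusion criteria admit "Mothers of preschool children who agree to participate and provide consent", and Ethical considerations list "Informed consent from each child's guardian". Inclusion criteria also require "Children and mothers who can attend all educational sessions".

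The two group descriptions give children one visit in the conventional arm and four in the non-conventional arm. The non-conventional arm adds a weekly online game from home for 3 months. The trial is called single-blinded, and the examiners are the only party named as blinded. Concealment of the toss is not mentioned.

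**The concern.** When whole classes are randomised, the start of the intervention is the wrong anchor for baseline. What protects the comparison is that pairs are enrolled and measured before anyone knows the arm. Once the toss is made, everyone approached in that class is approached in an arm that may be known.

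Three things can then depend on the arm: whether a mother agrees, whether a pair is judged able to attend all sessions, and how a mother answers questions about her own knowledge, attitudes and practices. The first two decide who is in each arm. A difference created that way passes straight into the 3-month comparison. Neither the randomness of the toss nor the t-tests and chi-squared tests named under Data analysis remove it, and a larger sample does not shrink it.

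**Working it through.** No figure in the Protocol bears on this point, so the check is of timing statements, followed by an illustration of size.

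**Step 1. Each step and its stated anchor.**

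| Step | Protocol section | Anchor given | Placed before the toss? |
|---|---|---|---|
| Class allocation | Children level (sampling) | none relative to consent or baseline | – |
| Guardian consent | Inclusion criteria; Ethical considerations | none | not stated |
| Ability to attend all sessions | Inclusion criteria | none | not stated |
| Baseline plaque | Measurements | start of intervention | not stated |
| Mothers' questionnaire | Measurements | start of intervention | not stated |
| Background questionnaire | Measurements | start of the study, undefined | not stated |

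**Step 2. Which orders comply.** Order A: select classes, consent, baseline, toss, teach. Order B: select classes, toss, consent, baseline, teach. Both satisfy the anchors for consent, plaque and the mothers' questionnaire. Order B also satisfies the background questionnaire's anchor if the study is taken to begin with the education. Nothing elsewhere in the document excludes order B.

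**Step 3. What knowing the arm could change.**
- *Consent:* the arms differ in what is asked of the family, most clearly in the weekly home game.
- *Attendance criterion:* being able to attend all sessions means one children's visit in one arm and four in the other, so one criterion can screen the arms differently.
- *Mothers' baseline answers:* these are self-reported by mothers who are not named as blinded. A shift here does not enter a plain comparison of 3-month scores. It does enter change scores and the two objectives that measure the impact of each programme separately.
- *Plaque:* examiners are to be blinded, and children are not told the examination day. That partly protects the scoring. It does not protect which children are there to be examined.

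**Step 4. Illustrative size (all inputs assumed).** Let c1 and c2 be the consent proportions, c1 the larger. Suppose the c2 share is alike in both arms and the extra c1 − c2 are mothers who score D SD worse. The difference between arms before any education is then

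(c1 − c2) / c1 × D.

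With D = 0.5 SD:
- 80% versus 70%: (10/80) × 0.5 = 0.0625 SD.
- 75% versus 70%: (5/75) × 0.5 = 0.033 SD.

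If the lower consent is in the more demanding arm, this flatters the non-conventional programme. The sign reverses if consent is lower in the conventional arm.

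**The case against.** The strongest reply is that the Protocol nowhere says the toss comes first. A reader might infer it because the toss is described in the sampling section, ahead of data collection. The document does not support that inference, because its sections are not chronological: baseline is described after the full intervention, and consent after the data analysis. The background questionnaire also suggests contact with parents at an early stage. This stands. The defect is an open order, not a stated wrong one. It does not answer the point, because the anchor the plan does choose permits the harmful order.

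A reader might also infer that baseline plaque scores are themselves biased. Blinded examiners and unannounced examination days argue against that, so only the entry of children is at issue for plaque.

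The contrast in burden is softer than the visit counts suggest. Children are taught in regular school hours, and the Exclusion criteria section says that all children receive education even when not counted. A mother may therefore not be deciding on the visits at all. A lecture for mothers is described in general terms but listed only under the non-conventional group, so it cannot be counted firmly as a difference. The home game remains one. Where children are sampled within a class by random number, who is invited is protected, but who agrees is not.

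Finally, one might express the illustrated bias as a share of the effect the trial can detect. The Protocol gives 788 pairs, 80% power and alpha 0.05 but no effect size or SD, and any clustering by class would change the detectable effect. No such share can be supported. What mothers are told about the arms is also unknown, as the information sheet is not in the text reviewed.

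**Conclusion.** The point holds as a badly fixed order of procedures. The Protocol allows consent, the attendance judgement and the mothers' self-reported baseline to be obtained after the class's arm is known, and it provides no concealment to prevent this. Selective entry by arm is the main risk. A shifted maternal baseline is secondary, and biased plaque scoring is largely not the issue.

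The size of the bias cannot be derived from the document. The range of about 0.03 to 0.06 SD rests wholly on assumed consent gaps of 5 to 10 points and an assumed 0.5 SD difference in the mothers lost. The document does not show that the bias will occur. The change is worth making because it is cheap now, and bias from enrolment after allocation cannot be reliably repaired at analysis.

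**What to change.** In the allocation text and in Measurements, state one order: select classes; obtain guardian consent; settle eligibility, including ability to attend; complete the mothers' questionnaire and baseline S-OHI; close the class list; only then toss for the class. For the baseline measures, replace the anchor *before the intervention* with *before allocation*. Put the background questionnaire on the same anchor, since its present one is undefined. Assess the attendance criterion against the commitments of both arms, so that it means the same thing whichever way the toss falls.

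The cost is small. These steps are already planned, and no participants, visits or measurements are added. Arm-specific teacher preparation and scheduling can begin in a kindergarten only after its baseline is finished.

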#### Sample size:

The calculation of the sample size for this study was conducted using the OpenEpi (openepi.com). The expected sample size will be 788 mother-child pair at a power of 0.80 and an alpha error of 0.05. To increase the statistical power and account for dropout during the follow-up period, the sample size will be raised by 10%, resulting in an additional 78 mother-child pair. Thus, the total sample size of this study will be 866 mother-child pair. These participants will be divided equally into two groups conventional group and non-conventional group. Each group will consist of 433.

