#### In conducting level:

-Stratification, by applying public and private strata.

-Standardization, by applying stringent protocols, and by training and calibration of examiners.

-Check and measure the expected confounding factors.

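### An unrestricted coin toss per class is unlikely to give the stated 433 per arm and leaves kindergarten and public/private sector unbalanced between arms

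*Protocol*

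**What the plan says.** Under the heading on selection at the children level, the protocol states: "Classes will be randomly allocated into the two study groups (conventional and nonconventional) using a a coin toss". The unit of allocation is therefore the class, and no restriction on the toss is described.

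The Sample size section gives a total of 866 pairs and then states: "These participants will be divided equally into two groups conventional group and non-conventional group. Each group will consist of 433".

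The Sampling technique section and the Al-Hofuf subsections use educational office, public or private sector and kindergarten size to choose kindergartens. The Confounding factors section lists, among its safeguards during conduct, "Stratification, by applying public and private strata". None of these passages links the strata to the allocation of classes.

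Random sampling of classes and children is described for the case where a kindergarten has more than the sample needs. It is not described as a way to equalise the arms after the toss.

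**The concern.** Two things that the document itself fixes do not fit together: a chance mechanism with no restriction, and an exact number per arm.

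The safeguard against confounding also stops short of the comparison it is meant to protect. Stratified sampling makes the sample resemble the region's kindergartens; it does not make the arms resemble each other. If one toss decides each class, a kindergarten with few classes can easily land wholly in one arm. Differences between kindergartens in sector, socioeconomic level or baseline hygiene then enter the arm difference by chance. With only ten or 14 kindergartens, this noise does not average out well.

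**Working it through.** **The plan's own figure.** 788 × 0.10 = 78.8, taken as 78. Then 788 + 78 = 866 and 866 / 2 = 433. The per-arm figure is reproduced.

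**Inputs.** From the protocol: 866 pairs; allocation by class; ten kindergartens (Sampling technique) or 14 (the sampling fraction under Private kindergartens). Not in the text: the number of classes in total or per kindergarten. The figure on recruited kindergartens and children is not visible in the copy reviewed. Assumptions: 36 to 44 classes, about 20 to 24 children each (866/44 = 19.7; 866/36 = 24.1), and 3 to 6 classes per kindergarten.

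**Arm size.** With K classes and one fair toss each, the number of classes in one arm is Binomial(K, 0.5). With equal class sizes, the SD of one arm's size is (866/K) × √K / 2 = 433/√K.

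- K = 36: SD 72.2, 95% range about 433 ± 141.
- K = 44: SD 65.3, 95% range about 433 ± 128.

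**Uneven class split.** Probability that the larger arm holds at least 60% of the classes:

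| K | 36 | 37 | 38 | 39 | 40 | 41 | 42 | 43 | 44 |
|---|---|---|---|---|---|---|---|---|---|
| 60:40 or worse | 24% | 19% | 26% | 20% | 27% | 21% | 16% | 22% | 17% |
| exact half split | 13% | 0 | 13% | 0 | 13% | 0 | 12% | 0 | 12% |

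An exact half split of classes still gives 433 per arm only if class sizes also balance.

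**Kindergarten wholly in one arm.** For c classes the probability is 2 × 0.5^c. For at least one of N kindergartens it is 1 − (1 − 2 × 0.5^c)^N.

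| Classes each | Per kindergarten | N = 10 | N = 14 |
|---|---|---|---|
| 3 | 25% | 94% | 98% |
| 4 | 12.5% | 74% | 85% |
| 5 | 6.25% | 48% | 60% |
| 6 | 3.1% | 27% | 36% |

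The cells consistent with 36 to 44 classes are 10 × 4 = 40 (74%) and 14 × 3 = 42 (98%). The others imply class totals outside that range, for example 10 × 3 = 30, and show how the risk moves.

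**Cost of unequal size alone.** The protocol states no effect size. 394 per arm corresponds to a standardised difference of about (1.96 + 0.84) × √(2/394) = 0.20, which is an inference. At 0.20 and ignoring clustering, power is 0.837 at 433:433 and 0.817 at 333:533.

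**Cost in precision.** A simulation assumed ten kindergartens, 2 to 5 classes of 22 children, a kindergarten intraclass correlation of 0.02 to 0.10 and no separate class effect. The variance of the arm difference under the toss was about 1.3 to 3.5 times that under allocation balanced within kindergarten. A class-level effect would shrink this ratio.

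**What restriction achieves.** Simulated 95% range of one arm's size, class sizes varying from 15 to 30 before scaling to a total of 866, odd class decided at random:

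| Kindergartens × classes | One toss per class | Balanced within kindergarten |
|---|---|---|
| 10 × 3 | 276–589 | 339–527 |
| 10 × 4 | 296–569 | 405–460 |
| 10 × 5 | 311–556 | 374–492 |
| 14 × 3 | 299–567 | 354–512 |

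One-arm kindergartens disappear wherever at least two classes are included.

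**The case against.** A coin toss is valid randomisation. It introduces no systematic bias, and unequal arms cost little power. This stands, and the point is therefore about precision and about a stated arm size that the method does not secure.

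The text does not exclude tossing once per pair of classes, or sampling children to a quota after allocation, either of which would bring the arms closer. That is true, but neither is stated, and both the method and the arm size are fixed in this document.

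A reader might infer that no adjusted analysis is planned. The document does not support this: the Data analysis section names t-tests and Chi-squared tests as included methods without ruling out others, the protocol plans to measure the expected confounders, and adjustment may be set out in an analysis plan not shown here. Nor can it be said that the tosses would go unrecorded; the protocol is silent on recording.

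Placing both arms in the same kindergarten invites contamination, since kindergarten teachers deliver the programme and the game can be reached by browser or app. This is a fair cost. It does not defeat the remedy, because allocation by class already mixes arms within kindergartens; blocking makes that somewhat more frequent.

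**Conclusion.** The point holds in a measured form. The unrestricted toss does not guarantee 433 per arm, is unlikely to deliver it, and does not carry the sampling strata into the allocation. In every scenario tabulated, the chance of at least one kindergarten lying wholly in one arm is 27% or more. The figures rest on assumed class counts and on a kindergarten count that the protocol gives as both ten and 14, so they are ranges; the direction does not depend on them.

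Two stronger readings should be avoided. Equal arms are not impossible under the toss: they can occur by chance. Balanced allocation would not remove both problems entirely: a single-class kindergarten always lies in one arm, and unequal class sizes or odd class counts leave some difference in arm size. The consequence is lost precision through chance confounding of arm with kindergarten and sector, not a biased trial.

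**What to change.** Replace the coin toss with restricted randomisation of classes. Block within each kindergarten where at least two classes are included, and balance single or odd classes within public/private and office strata. Draw the allocation from a computer-generated list, and reveal it for a kindergarten only after consent and baseline examination of its classes. The balance comes from the blocking; the computer list adds a record and makes concealment possible.

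In the Sample size section, state approximately 433 per group. Reconcile the number of kindergartens and state the expected number of classes, so that the blocks can be planned.

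The cost is a few lines of protocol text and a short program; a random number generator is already used for selection. Size imbalance is narrowed, not removed. The small downside is that more kindergartens will contain both arms, so the contamination risk already present with class-level allocation rises slightly.

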#### Children will be recruited proportionately between the three educational offices.

Sampling fraction= 866/13530= 0.064. The probability of each child to be selected is 6.4% Study weight= 13530/866= 16. Each child will represent 16 children.

### Kindergartens and children sampling

Figure 2. Recruited kindergartens and children from each educational office based on public and

# Data collection Oral health education will cover:

-Mouth component.

-Dental plaque.

-Consequences of plaque accumulation.

-Dental caries.

-Consequences of dental caries.

-Optimal oral hygiene practices.

-Role of preventive measures such as fissure sealant, fluoride, and importance of regular dental visits.

#### The oral health education program will be delivered by:

Specialized kindergarten teachers.

Teachers will undergo through a special, well-structured program for preparation, training and calibration.

For children, they will receive the program during regular school hours on weekdays.

**For mothers**, depending on what they prefer, the lecture will either be arranged in person or virtually via the Zoom online platform.

